2.2 Secondary Safety Endpoints

- Assess the short term (16 weeks) and long term (32 and 52 weeks) safety profile of secukinumab 300 mg s.c. in subjects with ARCI, NS and EI by monitoring for adverse events, SAE's, infections, or deleterious alterations in vital signs, other components of the physical examination, and clinical laboratory results

2.3 Exploratory Endpoints

- To explore secukinumab exposure/response relationship
- To explore the effect of treatment with secukinumab on laboratory parameters of interest (i.e. IL-17)

Product: Secukinumab

Protocol Number: CAIN457AUS05T

Date: 14 July 2018

16

- To explore change in mRNA expression levels of IL-17 and IL-17 induced genes as measured by gPCR
- To explore the alterations in bacterial and fungal microbiome before and after secukinumab therapy
- To explore self-administration of secukinumab
- To explore the relationship between disease severity and evidence for metabolic disease
- To explore the inter-rater reliability for severity assessments in the use for ichthyosis

2.4 Mechanistic Endpoints:

- Change in mRNA expression levels of IL17 and IL-17-induced genes as measured by qRT-PCR.

3. INVESTIGATIONAL PLAN

3.1 Study Design

To determine the efficacy and safety of IL-17 blockade with secukinumab on the clinical severity and morbidity of ARCI, NS and EI we propose to perform a 52 week study in 40 affected adults. The study will include an initial 16-week double-blind, randomized control phase in which 1:1 placebo: secukinumab is administered through week 12 with final evaluation of effects and safety at week 16. This double blind placebo controlled phase is followed by a 4 week crossover phase in which subjects who initiated placebo will be transitioned to active intervention, then a 32 week open-label phase. In this study, the “placebo,” which does not restrict bathing or emollient use, is “standard of care”, since many patients do not tolerate or use retinoids.

3.2 Study Centers

This study will be performed at two sites: the Department of Dermatology at Northwestern University Feinberg School of Medicine in Chicago and the Department of Dermatology at the Mt. Sinai School of Medicine in New York. Much of the clinical component will be performed and database housed at Northwestern University. Clinical research, statistical assessments, and biomarker tissue and molecular analyses of blood and skin will be performed at Mt. Sinai.

3.3 Study Organization

In this multiple Principal Investigator (PI) project, both PIs will be responsible for protocol development, consenting of subjects, performing skin biopsies, treatment and evaluation of subjects, review of adverse events, and reporting adverse events to the DSMB. Each site will have a project manager whose duties will include protocol development, grant administration for the individual study site, purchasing, case report form and source document design and development, and oversight of the project at the study site. The project manager at Northwestern will also be responsible for grant applications and yearly reports, and a liaison to the NIAMS grant administration (including the scientific officer, clinical coordinator, and program director) and the grant administrator at Mt. Sinai. An independent study safety monitor at each site will be contracted to perform review of consents, serious adverse events, and source verification on a quarterly basis throughout the study. This independent safety monitor in each institution will also assure that the data are correctly gathered, recorded, and put together concisely and accurately for prompt submission to the DSMB. The study safety monitors will work with the statistician to complete any unblinded statistical analysis for the DSMB reports. Thus, the audit function at each site is independent of the study research team. Data will be entered by study coordinators in a central REDCap database based at

Product: Secukinumab

Protocol Number: CAIN457AUS05T

Date: 14 July 2018

17

Northwestern (DCC). The Dermatology Clinical Trials Unit currently manages both international and national multisite REDCap databases. A designated data manager will manage and document all clinical data in REDCap, assuring the correct insertion and transfer of data, and aligning the institutions. The statistician will meet with the DCC every two months to discuss the progress of the study. In addition, an Executive Committee consisting of the Principal Investigators, the project managers and the study statistician will meet every other week by phone or Skype to address issues and ensure that all activities are moving forward in a coordinated manner.

3.4 Study Duration

The clinical portion of the study will include 1.5 years for subject accrual to allow up to 52 weeks of treatment duration, including followup. Complete data analysis, including limited gene expression analysis in skin, and manuscript preparation will require another 6 months, bringing the total anticipated study duration to 3 years.

3.4.1 Screening Period

The duration of the screening period will be from three to four weeks (21-28 days). Screening will be used to assess subject eligibility. Screening for infection or immunodeficiency (QuantiFERON, hepatitis B and C, HIV testing), Complete Metabolic Panel and CBC will be assessed at screening.

3.4.2 Double blind- Phase 1 (Baseline visit -- Week 15)

The double blind phase is defined as baseline visit [day 0] through week 15. At the start of the double blind phase, 6 eligible subjects with ARCI-CIE, 6 with ARCI-LI, 6 with EI and 6 with NS will be stratified by disease subtype in random blocks of 4 then randomized in a 1:1 ratio to one of two treatment arms (secukinumab 300 mg s.c. or placebo) via a randomization list. Neither subjects nor assessors will know to which group the subject is assigned. Subjects will be deemed eligible as per inclusion/exclusion criteria outlined in section 4. Secukinumab (300 mg) or placebo (2 syringes each) will be administered subcutaneously at Weeks 0, 1, 2, 3, 4, 8, and 12. Weeks 0, 4, 8, and 12 will be administered by the subject (or a doctor) in clinic during study visits. Weeks 1, 2, and 3 will be administered by the subject (or a caregiver) at home. Subjects will be examined at in clinic study visits at Weeks 0, 4, 8, and 12.

3.4.3 Cross-Over Phase-Phase 2 (Week 16 -- Week 19)

At Week 16, all subjects will be eligible to crossover into the second phase of the study, in which all subjects will receive secukinumab (300 mg). In order to maintain the initial blind and complete 4 months of treatment, subjects who had been randomized to secukinumab in the double blind phase will continue to receive secukinumab at a dose of 300 mg s.c. at Week 16. However, they will also receive three placebo injections at Weeks 17, 18, and 19, so that neither the subject nor the assessor knows if the subject had received secukinumab or placebo in the double blind phase. Subjects, who had been randomized to placebo in the double blind phase, will receive four doses of secukinumab at a dose of 300 mg s.c. at Week 16 to be administered on week 16, 17, 18, and 19 for loading. Weeks 16 will be administered by the subject (or a doctor) in clinic during study visits. Weeks 17, 18, and 19 will be administered by the subject (or a caregiver) at home. At Week 16, the primary endpoint will be assessed. Complete Metabolic Panel, and CBC at will be assessed at Week 16.

Product: Secukinumab

Protocol Number: CAIN457AUS05T

Date: 14 July 2018

18

3.4.4 Open Label Phase- Phase 3 (Week 20-Week 52 or End of Study)

At Week 20, subjects who have crossed over into the open label phase will receive 300 mg s.c. secukinumab at Week 20, 24, 28, 32, 36, 40, 44, and 48. Subjects will be examined at in clinic study visits at Weeks 20, 24, 32, 40, and 48. Weeks 20, 24, 32, 40, and 48 will be administered by the subject (or a doctor) in clinic during study visits. Weeks 28, 36, and 44 will be administered by the subject (or a caregiver) at home. The final in clinic study visit will be at Week 52 four weeks after the last dose for follow-up. Complete Metabolic Panel and, CBC at will be assessed at Week 32. Complete Metabolic Panel and CBC at will be assessed at Week 52 or End of Study.

3.5 Biomarker, Microbiome and Metabolic Analyses

In order to identify the molecular and cellular immune profile of the ichthyoses at baseline and identify treatment response biomarkers, we include blood analyses at screening (if on a systemic retinoid), baseline, Week 8, Week 16, Week 32, and Week 52. We will in parallel obtain punch biopsies (4.5 mm in diameter) from the upper arm (with the exception of week 8 to minimize biopsies for patients). If a patient terminates early, blood and biopsy will be obtained at that time. Of note, these patients have total body involvement (e.g., there is no “uninvolved skin”). The upper arm was chosen to be able to wrap with self-adherent wrap (such as Coban), since tape does not stick to ichthyotic skin.

Blood analyses of IL-17, IL-22 and IL-13 cytokines (by Singulex), chemokines (by MSD-a Th1, Th2 panel, and O-linked proteomics will be performed at screening (if on a systemic retinoid), baseline, Week 8, Week 16 or Early Termination visit, Week 32, and Week 52. Gene expression studies (RT-PCR and gene arrays) and immunohistochemistry of biopsy samples will be conducted. The expression levels of markers in different immune pathways, including: Th1 (IFN-gamma, CXCL10, STAT1), Th17 (IL-17, IL23p19, IL23p40, CCL20, CXCL1), Th2 (IL-13, IL-31, IL-10, CCL17, CCL18, CCL22), T22/IL-22 cytokine and IL-17/IL-22 regulated S100s genes (S100A7, A8, A9), will be evaluated using RT-PCR. We will also assess for modulation of IL-17 regulated antimicrobial peptides (i.e LL-37, elafin, lipocalin 2, hBD2, DEFB4B, inflammatory markers (i.e MMP12, S100A12), and innate immune genes (IL1b, IL-8) by RT-PCR. Skin expression studies will be correlated by cytokine/chemokine expression in the blood, as assessed by O-linked proteomic assessment of blood. Serum and RNA (Pax RNA) will be banked and frozen for later assessments based on unanticipated findings.

Skin infiltration by T-cells, DCs, and neutrophils will be assessed by immunohistochemistry. The following markers will be used: CD3 and CD8 for T cells, langerin for Langerhans cells, CD11c for myeloid DCs, neutrophil elastase to identify neutrophils, and lipocalin 2 (LCN2). Epidermal thickness will also be assessed by immunohistochemistry. Finally, gene arrays, particularly the Affymetrix U133A Plus 2 gene array platform, will also be performed. This same platform is being used in our other studies involving AD, psoriasis and alopecia areata (AA) patients.

Tape strips (noninvasive) will be taken at baseline, Week 8, Week 16 or Early Termination visit, Week 32, and Week 52 for lipidomic and proteomic assessments of the outer epidermis from the dominant arm (opposite to the nondominant arm used for TEWL, microbiome and biopsy measurements) at a site the clinically appears similar. A buccal swab will be collected and banked for future pharmacogenomics studies. Given our goal of determining whether the increases in skin Th17 cytokines reflect only a response to the barrier defect (for their antimicrobial effect) vs. pathogenic in driving inflammation – as

Product: Secukinumab

Protocol Number: CAIN457AUS05T

Date: 14 July 2018

19

well as to gauge alterations in microbial organisms as Th17 activation is suppressed by treatment, we will capture swabs for future microbiome assessment. Swabs for bacteria and fungi (including candida) will be obtained from the forehead, buttock and outer arm (near the biopsy site) at each visit, beginning at baseline. In flow studies of activated lymphocytes from patients with ichthyosis, we have recently found increases in blood levels of IL-22 cytokine, providing evidence of systemic activation of the IL-23/Th17 pathway. As a result, at baseline, Week 8, Week 16 or Early Termination visit, Week 32, and Week 52 we will also evaluate fasting lipids, glucose and CRP (as well as measure waist circumference) to assess for metabolic abnormalities.

4. SUBJECT ELIGIBILITY

Subjects should be at least 18 years of age with a clinical diagnosis of ARCI-LI, ARCI-CIE, EI or NS. The enrollment goal during the double-blind 16-week period will be at least 6 subjects each with ARCI-LI, ARCI-CIE, EI and NS (total 24), and an additional 16 patients, evenly divided into placebo and secukinumab groups and ideally (but less importantly) fairly evenly divided among ichthyosis subtypes (all comers will be included).

All screened subjects initially considered for this study will be documented. Pre-screening logs will be kept at each study site, and potential subjects will be contacted by the study site in closest proximity or with which the patient has previously been affiliated. If the subject is excluded from the study, reasons for exclusion will be documented in the pre-screening log.

4.1 Inclusion Criteria

Subjects are qualified for enrollment if they meet the following criteria:

- Subject has provided informed consent
- Subjects are at least 18 years of age or older at the time of screening.
- Female subjects must not be pregnant or breast-feeding.
- Female subjects of child-bearing potential with a negative urine pregnancy test and using at least one form of contraception (abstinence allowed).
- Subjects must have a confirmed diagnosis of ARCI-CIE, ARCI-LI, EI or NS (by genotype or willingness to be genotyped).
- Subjects must be clinically judged to be immunocompetent.
- Subjects will have no allergy to secukinumab, latex, or components of the product.
- Subjects will have baseline laboratory testing (normal or non-significant CMP and CBC, and negative for HIV, hepatitis B and C, QuantiFERON®-TB gold)
- Subjects must have an erythema score of at least 18 on IASI and an IASI-E score of 12 (at least moderate severity of erythema) at baseline.

4.2 Exclusion Criteria

Participants are ineligible for enrollment if they meet any of the following criteria:

- Subjects who are unable to give informed consent or assent.
- Subjects without a confirmed diagnosis of ARCI, EI, or NS.
- Subjects who have a known allergy to secukinumab or latex.
- Female subjects who are pregnant or who are considering becoming pregnant.

Product: Secukinumab

Protocol Number: CAIN457AUS05T

Date: 14 July 2018

20

- Subjects who have prior biologic use targeting IL-17A/IL-17 receptor A or IL-12/IL-23 or who have prior use of TNF-alpha blockers.
- Subjects who have used a systemic retinoid or systemic anti-ichthyosis agent within 4 weeks prior to initiation.
- Subjects who have used topical retinoids or keratolytics within one week prior to initiation.
- Subjects who have used emollient on the area to be biopsied in the previous 24 hours
- Subjects who have a history or diagnosis of inflammatory bowel disease
- Subjects who are on any systemic immunosuppressive agent (i.e. cyclosporine)

5. TREATMENT PROCEDURES

5.1 Investigational Treatment

The following study treatments will be used:

- Investigational drug
 - Secukinumab is a fully human IgG1κ monoclonal antibody that potently binds to IL-17A and not to other sequences or structurally related cytokines. In vitro, it blocks the ability of IL-17A to bind to its receptor and signal.
 - Secukinumab 300 mg, liquid formation in single-use prefilled syringes (two 150 mg pre-filled syringes for total of 300 mg dose)
- Reference therapy
 - Placebo to 300 mg secukinumab s.c. for injection will be provided in matching pre-filled syringes that contain a mixture of inactive excipients, matching the composition of the secukinumab 300 mg dose.
 - Placebo to secukinumab 300 mg, liquid formation in single-use pre-filled syringes (two syringes for placebo dose)

5.2 Double-Blind Phase-with four stratified diagnoses/subtype of EI, CIE, LI, and NS

At the baseline visit [day 0] subjects will be randomized into one of two treatment arms in a ratio of 1:1. Each arm will have at least 3 ARCI-CIE subjects, 3 ARCI-LI subjects, 3 EI subjects, and 3 Netherton syndrome subjects; there will be an additional 8 subjects in each arm with randomization designed to ensure that there is even matching by ichthyosis subtype.

5.2.1 Double-Blind Phase: Secukinumab arm

Subjects who meet eligibility criteria and have a normal baseline physical examination and laboratory testing will be enrolled in the double-blind phase. Each subject will receive 300 mg s.c. of secukinumab (administered in two pre-filled syringes) at Baseline (Day 0), Weeks 1, 2, 3, 4, 8, and 12.

Injections will be performed at the site for the initial visit to train subjects in proper aseptic and subcutaneous injection technique (per Novartis Package Insert 2016). Subjects will use the second syringe to demonstrate the ability to inject themselves. After this baseline instruction and observation of injection technique, subjects will be able to self-administer weekly or monthly injections.

We will contact subjects weekly by phone/Skype/FaceTime (subject will designate which is best) on weeks 1-3 to answer questions, assess compliance with administration, including proper disinfection of subject's hands and administration site, as well as to ensure safety and return at week 4. Subjects will keep a diary of administration dates and times (as well as use of emollients and baths), which will be

Product: Secukinumab

Protocol Number: CAIN457AUS05T

Date: 14 July 2018

21

reviewed at each appointment. All subjects who receive at least one dosage will be counted in the ITT population.

Week 16 will be the final endpoint for efficacy assessment of the double-blind phase.

5.2.2 Double-Blind Phase: Placebo arm

Subjects who meet eligibility criteria and have a normal baseline physical examination and laboratory testing will be enrolled in the double-blind phase. Each subject will receive 300 mg s.c. of placebo using two pre-filled syringes at Baseline (Day 0), Weeks 1, 2, 3, 4, 8 and 12.

Injections will be performed at the site for the initial visit to train subjects in proper subcutaneous injection technique. Subjects will use the second syringe to demonstrate the ability to inject themselves. After this baseline instruction and observation of injection technique, subjects will be able to self-administer weekly or monthly injections.

We will contact subjects weekly by phone/Skype/FaceTime (subject will designate which is best) on weeks 1-3 to answer questions, assess compliance with administration, including proper disinfection of patient's hands and administration site, and ensure safety and return at week 4. Subjects will keep a diary of administration dates and times (as well as use of emollients and baths), which will be reviewed at each appointment. All subjects who receive at least one dosage will be counted in the ITT population.

Week 16 will be the final endpoint for efficacy assessment of the double-blind phase and, at week 16, we will switch placebo-treated patients to secukinumab as all patients enter the open-label phase.

5.3 Crossover Phase

Because patients and investigators cannot know if they received secukinumab or placebo initially and the subjects who crossover need to receive weekly injections in the first month, all subjects will receive secukinumab 300mg at Week 16, followed by 3 weekly (week 17, 18, 19) administrations (2 syringes) of either placebo (if on secukinumab originally) or secukinumab (if previously on placebo).

5.3.1 Open Label Phase

All subjects will then continue with injections of secukinumab 300mg at week 20 and every 4 weeks thereafter through 48 weeks, with the final assessment at 52 weeks (Appendix 1). In person study visits will occur at Weeks 20, 24, 32, 40, 48, and 52.

5.4 Treatment Assignment, Randomization

At the baseline visit [day 0] eligible subjects will be randomized. A randomization number will be assigned to the subject which will be used to link the subject to a treatment arm.

Subject Identification

Subjects are numbered sequentially. Each subject will be assigned a unique number and will keep this number for the duration of the study. Subject numbers will not be reassigned or reused for any reason. Subjects should be identified only by their assigned identified code number. The investigator must maintain a subject master log linking the subject number to the subject's name. The investigator must follow all applicable privacy laws in order to protect a subject's privacy and confidentiality.

Randomization

Product: Secukinumab

Protocol Number: CAIN457AUS05T

Date: 14 July 2018

22

A centralized randomization system will be implemented at NU. After fulfilling the enrollment criteria, study participants will be randomized on day 0/baseline to secukinumab or placebo in a 1:1 ratio. Randomization will be stratified by disease subtype (ARCI-CIE, ARCI-LI, EI and NS) in random blocks of 4. We will not stratify by center due to the small sample size.

Codes will be sent from the data coordinating center (NU) and distributed to a licensed pharmacist at each study site. Records of the code/seed used to generate the randomization will be kept. The pharmacy and data management personnel will keep clinical Investigators blind through the study until all clinical data has been collected and recorded. A revision and quality control assessment of the collected data will be carried out. Once all data quality issues are sorted out, the data analysis stage will start and investigators will be unblinded. Laboratory personnel conducting assays for the mechanistic studies will be blinded.

5.5 Treatment Blinding

Subjects, investigator/site staff, individuals performing the assessment will not know the treatment assignment for individual subjects. This will be assured via the following methods:

- The randomization schema will be kept confidential until implementation.
- During the trial, all study personnel will be kept blinded except for the pharmacist.
- In order for study participants to remain blinded, a research pharmacist at each site will be assigned the responsibility of an unblinded dispenser and give the test article to the investigator or designee for administration.
- The research pharmacist may not administer the test article to study subjects.
- Contact between the unblinded dispenser and study subjects would be kept to a minimum.
- The investigator, study coordinator, and any study participants other than the unblinded dispenser must not be allowed to know the test article assigned to any study subject and must not be allowed to see the randomization chart, test article containers, or treatment records.
- The packaging, labeling, schedule of administration and appearance of secukinumab and placebo will be identical.

Unblinding

In case of an emergency, when knowledge of the test article assignment is required for the medical management of an individual subject, the subject will be unblinded. The code should be broken only in the event of a medical emergency, when knowing the treatment assignment is absolutely necessary. The investigators will notify the DSMB within 24 hours after determining that it is necessary to unblind the treatment assignment. The DSMB can also decide to unblind. The investigator must also indicate in source documents and in the case report form that the blind was broken and provide the date, time, and reason for breaking the blind. Any AE or SAE associated with breaking the blind must be recorded and reported as specified in this protocol.

A clinical data manager will assemble all the subject data by groups (treatment versus placebo) and the data safety monitoring board or the biostatistician may request the unblinding of subject treatment assignment for analyzing safety data, upon the appearance of unequal adverse events.

5.6 Dispense and Use of Investigational Treatment

5.6.1 Dispensing the Investigational Treatment

Product: Secukinumab

Protocol Number: CAIN457AUS05T

Date: 14 July 2018

23

Both study sites will be supplied by Novartis with secukinumab and placebo.

Secukinumab (AIN457) and placebo syringes from Novartis will be shipped to a designated, licensed pharmacist at the investigational pharmacy of each study site. The blinded study drug will be supplied as AIN457 150mg/1ml or placebo with 2 syringes per box. A removable tear-off label will be found on each box that identifies whether the box contains active drug or placebo. The Pharmacy will remove that label before the syringes are dispensed. Only the pharmacy staff and unblinded DCC staff will be aware whether the subject is receiving active drug or placebo for the blinded portion of the study. The subject and research physician will be blinded until completion of the study. The randomized code will be broken in the case of a Serious Adverse Event and unblinding for an individual subject may occur.

Open label drug will be provided for the open label portion of the study as Cosentyx ® 150mg/1ml with one syringe per box.

When delivery of a test medication is received at the investigational site, the Pharmacist, or a member of their staff specifically authorized and delegated by the Investigator, will check for accurate delivery and acknowledge receipt by signing (or initialing) and dating the required documentation and returning it as instructed. The date, time and condition of the package should also be documented at the time of receipt. A copy of this documentation will be retained for the Investigator file. Packaging, syringes, and medication appearance will be identical with the exception of the unique medication number on the label of the treatment packaging. This individual must store the treatment according to instructions specified on the packaging. An accurate record of the shipment and dispensing of these study agents will be kept by the respective pharmacist at each site. All unused study material will be returned by study subjects to the dispensary site.

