7.3 Serious adverse events

7.3.1. Definition of SAE

A serious adverse event (SAE) is any adverse event which:

- is fatal or life-threatening
- results in persistent or significant disability/incapacity
- constitutes a congenital anomaly/birth defect
- requires inpatient hospitalization or prolongation of existing hospitalization, unless hospitalization is for:
 - routine treatment or monitoring of the studied indication, not associated with any deterioration in condition
 - elective or pre-planned treatment for a pre-existing condition that is unrelated to indication under study and has not worsened since signing the informed consent
 - treatment on an emergency outpatient basis for an event not fulfilling any of the definitions of a SAE given above and not resulting in hospital admission
 - social reasons and respite care in the absence of any deterioration in the subject's general condition
- is medically significant, i.e., defined as an event that jeopardizes the subject or may require medical or surgical intervention

All malignant neoplasms will be assessed as serious under “medically significant” if other seriousness criteria are not met.

Life-threatening in the context of a SAE refers to a reaction in which the subject was at risk of death at the time of the reaction; it does not refer to a reaction that hypothetically might have caused death if more severe or ongoing.

Medical and scientific judgment should be exercised in deciding whether other situations should be considered serious reactions, such as important medical events that might not be immediately life threatening or result in death or hospitalization but might jeopardize the subject or might require intervention to prevent one of the other outcomes listed above.

Examples of such events are intensive treatment in an emergency room or at home for allergic bronchospasm, blood dyscrasias or convulsions that do not result in hospitalization or development of dependency or abuse.

Any suspected transmission via a medicinal product of an infectious agent is also considered a serious adverse reaction.

All AEs (serious and non-serious) are captured on the case report form; SAEs also require individual reporting to DSMB and to Novartis Medical Affairs as per Section 7.2.2.

Product: Secukinumab

Protocol Number: CAIN457AUS05T

Date: 14 July 2018

32

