9.2. Subject Demographics and Other Baseline Characteristics

Descriptive statistics of demographics and other baseline characteristics will be presented for all subjects. Demographics include age, sex, race, ethnicity, and skin type. Other baseline characteristics include height, weight, and vital signs, concurrent diagnoses (from medical history and indications for concomitant medication), concomitant medications, and previous treatments.

9.3. Efficacy Analyses:

All data will be analyzed after the 16-week double blinded portion of the study is completed. However, all patients and blinded study personnel will remain shielded from any information regarding the data after these analyses until the conclusion of the study.

Analysis of primary efficacy endpoint

The primary efficacy endpoint is the change from baseline to week 16 in the composite IASI score. Differences in change over time in the composite IASI score between treatment and placebo will be assessed using a mixed-effect model. The model will include treatment and treatment-by visit interaction as fixed effects and study subjects as random effects. Orthogonal contrasts will be used to test differences in the treatment effect at the different time points. This model produces unbiased treatment effect, even if

Product: Secukinumab

Protocol Number: CAIN457AUS05T

Date: 14 July 2018

35

some subjects have missing values (provided that the missing data is missing at random). Besides the change in the composite IASI score, final results will be presented as percent changes from baseline, calculated from the least square means of the model above (Vickers et al, 2001).

Analysis of primary safety endpoint

Safety analyses will be presented rates of bacterial or fungal mucocutaneous infection in each treatment group from baseline through week 16. The rate of infections will be compared using poisson regression. The proportion of subjects experiencing bacterial or fungal mucocutaneous infection during the study period in each treatment group will also be reported and compared using a Fisher exact test.

Analysis of secondary efficacy endpoint

We anticipate that, given the small sample size, a formal subgroup analysis (for ARCI-LI vs ARCI-CIE vs. EI vs. NS) will not be possible. However, we will report means and 95% confidence interval to descriptively compare the performance of the treatment across the four subgroups.

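### Section 5.6.1 breaks the code for any serious adverse event, which conflicts with the narrower rule in Section 5.5

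*Combined protocol and SAP*

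**What the plan says.** Four places in the protocol bear on when an individual assignment may be revealed.

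- **Section 5.6.1 (dispensing):** "The randomized code will be broken in the case of a Serious Adverse Event and unblinding for an individual subject may occur". The first clause is mandatory and sets no emergency or necessity condition. The second is permissive.
- **Section 5.5 (blinding, under Unblinding):** "The code should be broken only in the event of a medical emergency, when knowing the treatment assignment is absolutely necessary". Two discretionary routes follow. One is "The DSMB can also decide to unblind". By the other, the DSMB or the biostatistician "may request the unblinding of subject treatment assignment for analyzing safety data, upon the appearance of unequal adverse events".
- **Section 7.3.2 (SAE reporting):** follow-up information on an SAE is to include whether or not a code break took place, and whether the subject stayed in the trial or left it.
- **Section 7.2 (unblinding and follow-up):** when an adverse event forces early termination, the study team documents which treatment the subject was receiving. No time for this is given, and no link to the 5.5 criteria.

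Section 7.3.1 defines an SAE broadly. Besides fatal and life-threatening events, it covers inpatient hospitalization (with exceptions) and lasting disability. It also states: "All malignant neoplasms will be assessed as serious under" the medically-significant criterion when no other criterion applies.

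**The concern.** Sections 5.5 and 5.6.1 are adjacent and give different triggers for the same act. Under one, an SAE suffices. Under the other, an SAE by itself is not a trigger. No section states which prevails. The wider rule also sits in the dispensing section, which pharmacy staff, who hold the assignments, are likely to consult.

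The blind matters here because of how the endpoint is measured. Section 9.3 states: "The primary efficacy endpoint is the change from baseline to week 16 in the composite IASI score". Appendix 2 builds that score from a physician's 0-4 grades of erythema and scaling in four body regions, so the result depends on judgment. Section 3.3 has the principal investigators treat subjects, evaluate them and review their adverse events. A code result released because of an SAE could therefore reach someone who grades the endpoint. A break that patient care did not require would put the blind at risk for no benefit.

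**Working it through.** The plan gives no figure on this point and no arithmetic applies. The check sets the two rules against the kinds of event that 7.3.1 calls serious.

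| Event | 5.6.1, first clause | 5.5 |
|---|---|---|
| SAE that is an emergency in which care depends on knowing the assignment | Break | Break |
| SAE without that need | Break | No break, unless the DSMB decides to unblind or a request follows an imbalance in adverse events |

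The rules agree on the first row and differ on the second. The next question is whether the second row contains real cases.

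1. **Malignancy.** Under 7.3.1 every malignant neoplasm is an SAE. A new diagnosis need not be an emergency that turns on whether the subject had secukinumab or placebo.
2. **Admission for a skin infection.** Inpatient hospitalization makes it an SAE, outside the listed exceptions. Section 7.1 says mucocutaneous infections are treated by standard measures. Section 5.6.3 does not make a skin infection needing antibiotics a reason to stop study drug or leave the study. Such an event can be managed without the code.

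So the second row is not empty, and the conflict is one of substance.

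The last question is which rule was meant. Section 7.3.2 asks the SAE follow-up report to say whether a break happened. If every SAE broke the code, that item could have only one answer. It is informative only if some SAEs leave the code intact, as under 5.5. The permissive second clause of 5.6.1 points the same way. Both support 5.5 as the intended rule, though only by inference.

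Section 7.2 does not fit cleanly with either rule. An adverse event can require early termination without being an emergency, and possibly without being serious. If the assignment is documented at that time, this is a further route to unblinding that 5.5 does not list. If it is documented after study unblinding, there is no conflict. The text does not say which.

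**The case against.** The strongest reply is that the protocol, read as a whole, already favors discretionary unblinding. Section 5.5 is the section on blinding, with its own text on trigger, notification and documentation. Section 5.6.1 is about drug supply, and its one sentence on the matter ends permissively. Section 7.3.2 assumes that some SAEs leave the code unbroken. Nor is a decision-maker missing: under 5.5 the investigators determine that unblinding is necessary and notify the DSMB within 24 hours, and the DSMB may act on its own.

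Most of this stands, and it limits the point. It does not remove it. Even as a permission, 5.6.1 would allow a break for any SAE, where 5.5 allows an investigator's break only in an emergency.

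Three stronger readings are tempting, and the documents do not support them.

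- **That 5.6.1 also contradicts the general blinding statements.** Section 5.6.1 says "The subject and research physician will be blinded until completion of the study", and 5.4 says pharmacy and data management staff "will keep clinical Investigators blind through the study until all clinical data has been collected and recorded". These are general rules, and any code break is an exception to them, including the emergency break in 5.5. They add nothing to the conflict.
- **That each such break costs week-16 data.** Section 5.7 lists emergency unblinding as a reason to stop treatment, and a subject who stops has an end-of-study visit and is then discontinued. It does not say that a break for a non-emergency SAE counts as emergency unblinding.
- **That the raters would be told.** Section 5.6.1 does not say who receives the result, and 5.5 states that those performing assessments do not know the assignments. Exposure of a rater is a risk, not a stated consequence.

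**Conclusion.** The conflict is real and should be corrected. Section 5.6.1 makes any SAE a trigger. Section 5.5 does not, and 7.3.2 indicates that 5.5 is what was intended. Staff who followed 5.6.1 literally would break the code for subjects whose care does not require it, in a trial with a rater-graded week-16 endpoint.

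The size cannot be computed, because the documents give no expected SAE rate. For the primary endpoint, only some SAEs matter: those before the week-16 rating, outside the 5.5 criteria, and handled by staff who apply 5.6.1 over 5.5. A reader might express one unblinded subject as a share of the 40 randomized. That ratio measures neither bias nor loss of power, so no percentage is offered. A reader might also infer that the plan requires unblinding at every SAE. Sections 5.5 and 7.3.2 do not support that for the plan as a whole.

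The conclusion rests on two assumptions: that some SAEs under 7.3.1 can be managed without knowing the assignment, and that staff may act on 5.6.1 as written.

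**What to change.** In 5.6.1, replace the sentence on SAEs with: *An SAE alone does not break the code; unblinding follows Section 5.5.*

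In 7.2, add that when an adverse event leads to early termination, documenting the assignment waits until study unblinding, unless a criterion in 5.5 is met. Without this, 7.2 could still be read as a separate route to the assignment.

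The cost is one sentence replaced and one added, with submission to the IRB under 11.1. If the change is judged to affect safety or validity, 11.1 also requires approval by the IRB and Novartis Medical Affairs before it takes effect. Emergency access to the code and the DSMB's powers stay as they are. No visit, staff role, sample size or analysis changes.
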